6.2 PREPARATION/HANDLING/STORAGE/ACCOUNTABILITY

6.2.1 ACQUISITION AND ACCOUNTABILITY

Investigational Drug Service stocks the Pyxis machine with the study drug. it uses real time automated biometric safety protocols to ensure only those able to administer the study drug are allowed to remove it

6.2.2 FORMULATION, APPEARANCE, PACKAGING, AND LABELING

PI attached to IRB application. it is a brown ampule with 10mg total in the vial.

6.2.3 PRODUCT STORAGE AND STABILITY

It is stored in the Pyxis machine as per requirements

6.2.4 PREPARATION

After removal from the Pyxis machine the study drug is steriley drawn up into a syringe and labeled "study drug". This is then handed off to a different member of the study team to administer. The remainder is returned to the drug lockbox as per protocol

6.3 MEASURES TO MINIMIZE BIAS: RANDOMIZATION AND BLINDING

All patients presenting for VD are eligible and the clinical teams are trained in implicit bias and have had special education from the research team for this study. Given the randomization we cannot demand

that any specific group be targeted for recruitment. We want an equitable and balanced sample for our study.

6.4 STUDY INTERVENTION COMPLIANCE

Each step is recorded in either the datasheets or Pyxis logs. After the administration all that remains is data collection from the patients. Given that we contact patients at the required times we expect a high level of compliance.

6.5 CONCOMITANT THERAPY

6.5.1 RESCUE MEDICINE

Any patients on opiates or with an allergy to morphine are excluded and as such there is no risk for synergistic effects of the study drug. As per our CD protocol, we provide the same rescue doses of medications for morphine including ondanstetron, diphenhydramine, and nalxone all as needed.

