1 PROTOCOL SUMMARY

1.1 SYNOPSIS

Title:	Duramorph Study Design: Prospective, Randomized Double Blinded
Study Description:	Prospective double blind randomized control trial
Objectives:	Primary Objective: Analyze impact of epidural morphine on pain management for vaginal delivery VD Secondary Objectives: Analyze impact of epidural morphine on recovery and depression
Endpoints:	Primary Endpoint: Opiate consumption at 24 hours Secondary Endpoints: Pain score at 24 hours, obstetric recovery score at 24 hours, Edinburgh post partum depression scale at 6 weeks, breast feeding success at 1 week
Study Population:	Pregnant women over 18
Phase:	4
Description of Sites/Facilities Enrolling Participants:	KP2 Labor floor at Mount Sinai Hospital
Description of Study Intervention:	Epidural morphine 2mg vs placebo
Study Duration:	4 years
Participant Duration:	6 weeks

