1.2 SCHEMA

1. Obtain consent
2. 1 hour delivery administer study drug or placebo
3. 24 hours after collect data on opiate administration, pain score, and recovery score
4. 1 week after administration call patient inquire about breast feeding
5. At 6 weeks after administration call patient and administer post partum depression screen

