2.3 RISK/BENEFIT ASSESSMENT

2.3.1 KNOWN POTENTIAL RISKS

Risks can include nausea, vomiting, itching, respiratory depression

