2.3.3 ASSESSMENT OF POTENTIAL RISKS AND BENEFITS

Benefits include less oral and IV opiate use which also cause nausea, itching and respiratory depression. Benefits may also include a faster recovery and more breast feeding. The risks of this dose of morphine are small and have been used for cesarean delivery for decades.

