8 STUDY ASSESSMENTS AND PROCEDURES

8.1 EFFICACY ASSESSMENTS

At 24 hours we will get a likert pain score, as well as a recovery score. We will also obtain opiate consumption for this time.

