9.2 SAMPLE SIZE DETERMINATION

Based on other works it was determined that for a 25% reduction in opiate utilization we needed 60 patients for each group. To account for drop off we will recruit 150 patients per group for a total of 300 patients

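### Section 9.4.4 rules out any safety analysis, so no by-arm report of respiratory depression, naloxone use, nausea or itching is planned; secondarily, the no-synergy statement in 6.5.1 does not follow from an entry exclusion

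*Combined protocol and SAP*

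**What the plan says.** **Safety analysis.** The whole entry under section 9.4.4 (Safety Analyses) is N/A. Sections 9.4.2 and 9.4.3 assign tests to efficacy endpoints only. Section 9.4.1 gives a general rule by variable type and names no safety variable.

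**Harms the protocol recognises.**
- Section 2.3.1: "Risks can include nausea, vomiting, itching, respiratory depression".
- Section 8.3.1 names nausea and itching as adverse events. Section 8.3.3.3 expects both and foresees no respiratory depression.
- Section 8.3.2 defines the serious event as respiratory depression that needs naloxone. Section 7.1 halts the trial for review after respiratory depression of any kind.
- Section 3 justifies the primary endpoint by the side effects of opiates, and section 2.3.3 argues: "Benefits include less oral and IV opiate use which also cause nausea, itching and respiratory depression".

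**How events are captured.** Under 8.3.5, adverse events come from participants at follow-up, or from the clinical team if they are raised. Under 8.3.6, every participant is watched for respiratory depression, and all cases go to committee review.

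**Synergy.** Section 6.5.1, under Concomitant Therapy, begins "Any patients on opiates or with an allergy to morphine are excluded". It then concludes that such patients "are excluded and as such there is no risk for synergistic effects of the study drug". The synopsis gives "Primary Endpoint: Opiate consumption at 24 hours", the schema says "24 hours after collect data on opiate administration, pain score, and recovery score", and section 8.1 adds "We will also obtain opiate consumption for this time".

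**The concern.** The case for epidural morphine here is partly a trade of harms: fewer systemic opiates, hence fewer of their side effects, against the side effects of the epidural dose itself. A reader of the results will want both sides of that trade by arm. The plan sets out the efficacy side and marks the safety side as not applicable. If the plan is followed literally, the report could show lower opiate use with no matching account of nausea, itching, respiratory depression or naloxone use.

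The sentence in 6.5.1 raises a related but smaller issue. It offers an unqualified assurance about combined opioid effects, and its reason concerns who enters the trial, not what is given after the dose. Anyone relying on the protocol for the risk picture would be told that a risk is absent when the design does nothing to remove it.

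**Working it through.** **Step 1. Is a by-arm safety report planned anywhere?**

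| Section | What it provides | By-arm summary? |
|---|---|---|
| 7.1 | Halt and review on any respiratory depression | No |
| 8.3.3.2, 10.1.6 | Each case examined | No |
| 8.3.4, 8.3.6 | Monitoring, equipped recovery areas, committee review | No |
| 9.4.1 | Test by variable type, no safety variable named | No |
| 9.4.2, 9.4.3 | Efficacy endpoints | No |
| 9.4.4 | N/A | No |
| 10.1.8 | Respiratory depression investigated by the departmental QI committee | No |

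The safeguards work on single cases. None yields a count and denominator per arm. The general rule in 9.4.1 cannot be read as overriding an explicit N/A in the section made for the purpose.

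**Step 2. Which events belong in the table?** Section 7.1 (any respiratory depression) and 8.3.2 (only if naloxone is needed) define different events, the first broader than the second, so they need separate rows. Naloxone use is a third row. Nausea and itching come from 8.3.1 and 8.3.3.3, and vomiting from 2.3.1.

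**Step 3. What would the table say about a rare event?** The plan states no safety figure to reproduce. Inputs: n = 150 per group (9.2), all randomized participants analysed (9.3). Exact (Clopper-Pearson) two-sided 95% interval for one arm:

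- 0 events: lower limit 0; upper limit = 1 − 0.025^(1/n) = 1 − 0.025^(1/150) = 0.0243, or 2.4%.
- 1 event: lower limit = 0.025 quantile of Beta(1, 150) = 0.00017; upper limit = 0.975 quantile of Beta(2, 149) = 0.0366. The interval is 0.02% to 3.7%.

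So if the expectation in 8.3.3.3 is met and no case occurs, rates up to 2.4% in that arm remain compatible with the data. These figures describe the precision of the proposed table. They say nothing about whether synergy occurs.

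**Step 4. Does the inference in 6.5.1 follow?**

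- Premise: an exclusion applied at entry (5.2 and 6.5.1).
- Conclusion: no risk of synergy with the study drug.
- What happens after dosing: systemic opiate use over the next 24 hours is the primary endpoint (1.1, 1.2, 8.1). No section bars, caps or spaces those opiates. The sample size was set so that "for a 25% reduction in opiate utilization we needed 60 patients for each group", which targets a reduction and not elimination, so some use in the active arm is expected.
- Shared harm: respiratory depression is listed for the study drug (2.3.1) and for oral and IV opiates (2.3.3).

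The premise does not reach the period in which the two exposures overlap, so the conclusion does not follow from it.

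**The case against.** **The gap is one of prespecification only.** Participants are randomized, all are monitored for respiratory depression, and cases are reported, so arm and denominator will be known. The same intervals could be computed when the trial is written up. This stands. A reader might infer that the safety data are lost or the rate unknowable, and the documents do not support that. What remains is that the plan, as written, rules the analysis out.

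**Participants are already protected.** A reader might also infer that respiratory depression goes unwatched. It does not: monitoring, equipped recovery areas, naloxone as needed, committee review and a halt on any case are all in the protocol, and none depends on the sentence in 6.5.1. This stands in full, and it limits the point to reporting and wording.

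**The sentence in 6.5.1 may concern only opiates already on board at dosing.** That is a fair reading of its premise. The conclusion is not limited in that way, though, and it sits under Concomitant Therapy. The stronger inference, that the sentence is false or that synergy will occur, also fails. The documents do not say whether the two effects add or interact. The statement is unsupported, not disproved.

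**Adverse event counts will be weak.** Under 8.3.5, nausea and itching are not said to be actively elicited on a schedule, so a table may undercount them. This stands as a caution on interpretation. It is no reason to leave them out, since they are the harms the protocol expects.

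**Conclusion.** The point holds as a modest correction that should be made. Section 9.4.4 leaves the trial with no planned by-arm report of any harm, although the primary endpoint is justified by opiate side effects and the protocol expects nausea and itching. The primary test and the sample size are unaffected.

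The 2.4% upper limit for no events assumes 150 participants per arm are randomized and assessed for respiratory depression. If a first case stopped the trial and it did not resume, the denominator would be smaller and the interval wider.

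The wording of 6.5.1 is secondary. Correcting it makes the risk statement accurate and alters no monitoring, review or stopping provision.

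**What to change.** 1. **Section 9.4.4.** Replace N/A with a descriptive tabulation by randomized arm of:
   - respiratory depression, any;
   - respiratory depression requiring naloxone, as a separate row;
   - naloxone use;
   - nausea, vomiting and itching.

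   Give counts, denominators and exact 95% confidence intervals. No hypothesis test is needed. Add a note that nausea, vomiting and itching are collected as described in 8.3.5, so their counts should be read with caution.
2. **Section 6.5.1.** Delete the inference about synergy. State that systemic opiate use after the epidural dose is expected, that it carries an overlapping risk of respiratory depression, and that this is handled by the monitoring in 8.3.4 and 8.3.6.
3. **Opiate use before an event.** If it is described, keep it in the case narrative. It arises after randomization, so subgroups formed on it should not be compared.

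**Cost.** One small table and a protocol amendment, which the compliance statement at the front of the protocol says needs IRB approval before use. If the consent form changes, a decision on re-consent is also needed. Any case narratives may need a chart look-up for dose times, which the protocol does not promise to record.

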7 STUDY INTERVENTION DISCONTINUATION AND PARTICIPANT DISCONTINUATION/WITHDRAWAL

7.1 DISCONTINUATION OF STUDY INTERVENTION

Should we experience any cases of respiratory depression we will stop the study and review the case.

7.2 PARTICIPANT DISCONTINUATION/WITHDRAWAL FROM THE STUDY

Participants may withdraw from the study at any time by notifying the study team and/or the PI either verbally or in written form.

7.3 LOST TO FOLLOW-UP

Given that one of our endpoints is 6 weeks out we expect to lose some patients to follow up. This will impact our findings, however, our study is powered for our primary endpoint which is opiate consumption at 24 hours. We expect little or no followup loss for this endpoint.

8 STUDY ASSESSMENTS AND PROCEDURES

8.1 EFFICACY ASSESSMENTS

At 24 hours we will get a likert pain score, as well as a recovery score. We will also obtain opiate consumption for this time.

8.2 SAFETY AND OTHER ASSESSMENTS

At one week we will ask patients about breast feeding. At 6 weeks we will ask about depression

8.3 ADVERSE EVENTS AND SERIOUS ADVERSE EVENTS

8.3.1 DEFINITION OF ADVERSE EVENTS (AE)

Adverse events include nausea and itching

8.3.2 DEFINITION OF SERIOUS ADVERSE EVENTS (SAE)

Serious adverse event would be respiratory depression requiring naloxone administration

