4.4 END OF STUDY DEFINITION

Patients complete their involvement after their 6 weeks post partum depression screen

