8.3.3 CLASSIFICATION OF AN ADVERSE EVENT

Classification of an adverse event is based on symptomatology type as described above.

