8.3.3.1 SEVERITY OF EVENT

As above, severity is determined by need to administer rescue medications and type.

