8.3.3.3 EXPECTEDNESS

We expect to have cases of nausea and itching, we anticipate no cases of respiratory depression

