8.3.5 ADVERSE EVENT REPORTING

We receive reports from patients about their AEs on follow up or from the clinical team if they bring it up.

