8.3.6 SERIOUS ADVERSE EVENT REPORTING

All patients are monitored for respiratory depression. All cases of this are reported to our internal PI committee and reviewed independently.

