8.4.2 UNANTICIPATED PROBLEM REPORTING

At any time any participant, clinical team member, or study team member can report an event to the PI.

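### The SAE definition in section 8.3.2 covers one event only, so a death, life-threatening event, hospitalization or lasting disability from any other cause would not be classified as serious

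*Combined protocol and SAP*

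**What the plan says.** Section 8.3.2, headed as the definition of SAEs, consists of one sentence: "Serious adverse event would be respiratory depression requiring naloxone administration".

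The sections around it sort events in other ways:

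- 8.3.3: "Classification of an adverse event is based on symptomatology type as described above".
- 8.3.3.1: "severity is determined by need to administer rescue medications and type".
- 8.3.3.2 has the team look at every case and judge whether the study drug caused it.

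Reports come in under 8.3.5 ("We receive reports from patients about their AEs on follow up or from the clinical team if they bring it up") and 8.4.2 ("At any time any participant, clinical team member, or study team member can report an event to the PI"). Section 10.1.6 has the PI look at every AE and SAE.

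Review by a committee is described in two places. Section 8.3.6 reads: "All patients are monitored for respiratory depression. All cases of this are reported to our internal PI committee and reviewed independently". Section 10.1.8 leaves quality matters with the PI but sends respiratory depression to the departmental quality committee. Section 7.1 halts the study for a review if any respiratory depression occurs.

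**The concern.** A definition of seriousness decides which events are labelled and escalated. This one is tied to a single drug effect and a single treatment for it, so the outcome of an event plays no part. A participant could die, be readmitted or be left with a lasting deficit, and unless the cause was respiratory depression the event would fall outside the definition.

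Such events can arise within the trial's own follow-up. Section 4.4 says: "Patients complete their involvement after their 6 weeks post partum depression screen". Participants are telephoned at 1 week and 6 weeks, and AEs may be learned of at follow-up. A readmission mentioned in one of those calls is a plain example. At stake are the safety classification of the event and the level of review it receives. The primary endpoint, opioid use at 24 hours, does not depend on this definition.

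**Working it through.** No arithmetic applies: the point turns on wording, and the plan states no figure to reproduce. The check has two steps.

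**Step 1: look for outcome-based criteria.** The four sought are death, threat to life, new or prolonged hospitalization, and lasting disability.

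- 8.3.1 (AE definition): none. It gives nausea and itching as examples, with open wording.
- 8.3.2 (SAE definition): none of the four. Its wording is not open.
- 8.3.3 (classification): by type of symptom, not outcome.
- 8.3.3.1 (severity): by rescue medication. Section 6.5.1 names ondansetron, diphenhydramine and naloxone, and a grave event that calls for none of these has no clear place on that scale.
- 8.3.6, 7.1 and 10.1.8: each singles out respiratory depression.
- Opening compliance statement: cites ICH GCP and federal regulations but sets out no seriousness criteria.

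Result: none of the four criteria appears in the available text.

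**Step 2: run three events through the text.**

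| Event | SAE under 8.3.2? | Examination by team or PI | Committee or independent review stated? |
|---|---|---|---|
| Respiratory depression, naloxone given | Yes | Yes (8.3.3.2, 10.1.6) | Yes (8.3.6, 10.1.8), plus study stop (7.1) |
| Respiratory depression, no naloxone | No | Yes | Yes, same route, because 7.1, 8.3.6 and 10.1.8 do not depend on naloxone |
| Death, threat to life, hospitalization or lasting disability from another cause | No | Yes, if reported (8.3.3.2, 8.3.5, 8.4.2, 10.1.6) | None in the available text |

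In the second row only the label is affected; the event is still escalated. The third row holds the defect: the label is wrong, and no review by a committee or independent body is stated.

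**The case against.** Four arguments can be made for the plan.

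**The sentence may only name the SAE of concern for this drug.** Its conditional phrasing allows that reading, and it is unlikely that anyone meant to exclude deaths. But the section is headed as the definition, and 8.3.3.3 says "we anticipate no cases of respiratory depression", so the sentence is hardly a list of expected SAEs. Even on the generous reading, staff have no rule for deciding whether any other event is serious.

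**The plan commits to ICH GCP.** It does, but in unfinished template text that still contains a placeholder for the funding institute and a drafting instruction about options. A general commitment without criteria does not override a specific, narrower definition.

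**The events are not lost.** This stands. The AE definition is open, anyone may report to the PI at any time, each case is examined for relationship, and the PI looks at all AEs. Sections 8.3.7 and 8.4.3 also provide for telling participants. A reader might infer that the PI alone would ever review such an event. The documents do not support that, because 8.3.3.2 and 8.3.5 speak of the team receiving and examining cases. The team is not shown to be independent, but it is more than one person.

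**The main drug hazard is already well covered.** This also stands. It is a single dose in a Phase 4 trial, and respiratory depression triggers a stop and review beyond the PI. That limits the gap to other causes; it does not close it.

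**Conclusion.** Section 8.3.2 is wrong as written. This is more than missing detail, because applying the stated rule would misclassify events. The extent is textual: none of the four outcome criteria is present, and committee or independent review is stated for one type of event only.

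Confidence differs between the two parts. On the definition it is high: 8.3.2 is the only SAE definition in the available text. On the review route it is lower, because the section between 10.1.4 and 10.1.6 was not available and might say more about who reviews. That section lies outside 8.3, so it is unlikely to hold a different definition.

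A reader might also want to infer how likely the 300 planned participants are to include such an event. The documents give no rate for these events, so any probability would only reflect the rate assumed. The conclusion does not need one.

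**What to change.** Change the wording in three sections.

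- **8.3.2:** define an SAE as any untoward event that results in death, is life-threatening, requires new or prolonged hospitalization, or causes lasting disability. Keep respiratory depression that needs naloxone as a named SAE.
- **8.3.6:** extend the existing committee reporting and independent review to all SAEs, still including every case of respiratory depression.
- **10.1.8:** widen the exception so that all SAEs, as well as respiratory depression, go to the departmental committee.

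Section 7.1 can stay as it is. So can 8.3.3.1, since severity is a separate matter from seriousness.

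The cost is a few more events to report and review, by bodies the plan already names. The change governs how events that reach the team are labelled and escalated. It does not add a question about readmission or other grave events to the 1-week and 6-week calls, so it will not by itself find events that nobody reports.

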8.3.3 CLASSIFICATION OF AN ADVERSE EVENT

Classification of an adverse event is based on symptomatology type as described above.

8.3.3.1 SEVERITY OF EVENT

As above, severity is determined by need to administer rescue medications and type.

8.3.3.2 RELATIONSHIP TO STUDY INTERVENTION

We will examine each case and determine relationship to the study intervention.

8.3.3.3 EXPECTEDNESS

We expect to have cases of nausea and itching, we anticipate no cases of respiratory depression

8.3.4 TIME PERIOD AND FREQUENCY FOR EVENT ASSESSMENT AND FOLLOW-UP

Patients are monitored according to post partum protocols. The areas the patients recover are all equipped to manage patients after receiving neuraxial morphine.

8.3.5 ADVERSE EVENT REPORTING

We receive reports from patients about their AEs on follow up or from the clinical team if they bring it up.

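### Nausea, vomiting and itching are not asked about at any listed contact, and rescue drug use is not listed as data, so non-serious side effects will probably be under-counted and collected non-uniformly

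*Combined protocol and SAP*

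**What the plan says.** Section 2.3.1 sets out the known risks: "Risks can include nausea, vomiting, itching, respiratory depression". Section 8.3.1 defines the non-serious events more narrowly, "Adverse events include nausea and itching", without vomiting, and section 8.3.3.3 expects nausea and itching to occur. No rates are given.

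The collection rule is in section 8.3.5: "We receive reports from patients about their AEs on follow up or from the clinical team if they bring it up". The contents of the planned contacts are:

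- 24 hours (8.1): "At 24 hours we will get a likert pain score, as well as a recovery score. We will also obtain opiate consumption for this time". The schema (1.2) and the schedule of activities (1.3) list the same three items.
- 1 week and 6 weeks (8.2): "At one week we will ask patients about breast feeding. At 6 weeks we will ask about depression".

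Section 8.3.4, which should give the timing and frequency of event assessment, refers to routine post-partum protocols. Section 8.3.3.1 grades events as follows: "As above, severity is determined by need to administer rescue medications and type". Section 6.5.1 names the rescue drugs as ondansetron, diphenhydramine and naloxone.

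Respiratory depression has its own route. Section 8.3.2 defines the serious event: "Serious adverse event would be respiratory depression requiring naloxone administration". Section 8.3.6 has all patients monitored for respiratory depression and all cases reported and reviewed, and section 10.1.8 sends these cases to the departmental QI committee.

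**The concern.** The protocol expects nausea and itching and gives every participant a 24-hour contact, but lists no question about either symptom there. Whether an event is recorded then depends on what a patient mentions and on what ward staff pass on. Both vary between people for reasons unrelated to whether the event occurred.

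The benefit-risk argument in section 2.3.3 is at stake. It sets the side effects of epidural morphine against those of the oral and IV opiates it should spare, and names nausea and itching among the latter. That trade-off can be judged only if the symptoms are counted in the same way in every participant in both arms. With passive collection, a report of acceptable tolerability could partly reflect that nobody asked. The primary endpoint, opiate consumption at 24 hours, is not affected.

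**Working it through.** **Where an event could be picked up.** The protocol gives no figure for event rates, capture or safety power, so there is nothing to reproduce. The check is a comparison of sections.

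| Place | What it lists | Nausea, vomiting or itching asked? |
|---|---|---|
| 1.2 and 1.3, all time points | Opiates, pain, recovery, breast feeding, depression screen | No |
| 8.1, 24 hours | Pain score, recovery score, opiate consumption | No (recovery score items not given) |
| 8.2, 1 and 6 weeks | Breast feeding, depression | No |
| 8.3.4, timing and frequency | Routine post-partum protocols | No study-specific times |
| 8.3.5, reporting | Patients on follow-up; clinical team if they raise it | No fixed question or window |

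The contact after 24 hours is at 1 week, so a symptom first mentioned then is recalled about 6 days later (7 − 1).

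**Rescue medication.** Grading under 8.3.3.1 needs to know which rescue drug was given. No section makes this a collected item. Section 6.4 mentions datasheets and Pyxis logs, but it concerns compliance with the study drug.

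**What under-capture does.** Let p1 and p2 be the true event proportions on placebo and morphine, and let c be the fraction of events recorded, equal in both arms. Then:

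- observed difference = c·p2 − c·p1 = c·(p2 − p1), which shrinks in proportion to c;
- observed ratio = c·p2 / (c·p1) = p2/p1, which is unchanged.

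**Illustration.** Section 9.2 gives n = 150 per arm. All rates and capture fractions below are assumptions, as is the two-sided 5% test. The power of a two-proportion comparison (normal approximation) is

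Φ{ [d − 1.96·√(2·p̄(1 − p̄)/n)] / √[(q1(1 − q1) + q2(1 − q2))/n] },

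with q1 = c·p1, q2 = c·p2, d = q2 − q1 and p̄ = (q1 + q2)/2.

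- 30% v 15%, c = 1: p̄ = 0.225, so (0.15 − 1.96 × 0.0482)/0.0474 = 1.17 and power is 0.88.
- 30% v 15%, c = 0.5: observed 15% v 7.5%, p̄ = 0.1125, so (0.075 − 1.96 × 0.0365)/0.0362 = 0.10 and power is 0.54.

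| Assumed true rates | Capture | Observed difference (points) | Power |
|---|---|---|---|
| 30% v 15% | 100% | 15 | 0.88 |
| 30% v 15% | 70% | 10.5 | 0.71 |
| 30% v 15% | 50% | 7.5 | 0.54 |
| 30% v 15% | 30% | 4.5 | 0.34 |
| 20% v 10% | 100% | 10 | 0.68 |
| 20% v 10% | 50% | 5 | 0.38 |

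**If capture differed by arm.** Assume equal true rates of 20%, with 40% captured in one arm and 60% in the other. The observed rates are 0.20 × 0.40 = 8% and 0.20 × 0.60 = 12%, and a false difference would be declared about 21% of the time. Nothing in the documents shows that this will happen.

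**The case against.** Several points on the other side are sound and limit the claim.

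- **Respiratory depression.** A reader might infer that no adverse event is recorded unless someone raises it. Sections 8.3.6 and 10.1.8 rule this out for respiratory depression, one of the four named risks. The point is limited to nausea, vomiting and itching.
- **The clinical-team route.** A reader might infer that a woman who does not volunteer a symptom has no event on record. That goes too far, because staff who treat nausea or itching with a rescue drug know of the event and can report it. The route is unsystematic, and it favours treated events.
- **The wording of 8.3.5.** Receiving reports from patients on follow-up could include asking them. The text does not say so, and none of the contacts lists such a question, so staff who follow the protocol need not ask.
- **The recovery score.** Its items are not given, so it may cover some of these symptoms. Even so, no section uses it to record adverse events.
- **Uneven capture between arms.** This is a tempting inference that the documents do not support. The trial is double blind (4.1), and the drug is drawn up by one team member and given by another (6.2.4). If blinding holds, capture should be similar in both arms. It could diverge if side effects reveal the allocation, but that is a possibility only.
- **Section 8.2.** Its heading also covers other assessments, and adverse events have their own section, 8.3. The absence of these symptoms from 8.2 would therefore not matter if 8.3 supplied a timed question, but it does not.
- **The power figures.** They rest wholly on assumed rates and on a between-arm test that the protocol does not plan (9.4.4 is marked as not applicable). They show the direction and the proportional shrinkage, not the loss to be expected in this trial.

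**Conclusion.** The concern holds in a limited form. The protocol has no uniform, timed, solicited collection of nausea, vomiting and itching, and rescue medication, on which severity grading depends, is not listed as data. Under-counting is a reasonable inference from the rule as written, not a demonstrated fact, and its extent cannot be known from the documents.

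If capture is equal in both arms, any absolute difference is multiplied by the capture fraction and the ratio is unchanged. This weakens the benefit-risk comparison in section 2.3.3 but does not create a false difference. The change should be made before further participants reach the 24-hour contact, because symptoms not asked about then cannot be reliably recovered later. How events are analysed by arm is a separate matter, but any such table would be built on these counts.

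**What to change.** 1. Rewrite section 8.3.5 so that, at the existing 24-hour contact, the study team asks every participant in both arms the same fixed yes/no questions on nausea, vomiting and itching since study drug administration.
2. When opiate doses are extracted for the primary endpoint, also record each ondansetron, diphenhydramine and naloxone dose with its time and indication. This supplies the data that the grading rule in 8.3.3.1 needs.
3. Enter the respiratory depression events already captured under 8.3.6 in the study dataset.
4. Add these items to the schedule of activities (1.3) and to section 8.2, and reconcile the event list in 8.3.1 with the risks in 2.3.1, since vomiting appears only in the latter.

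The cost is a few more fields on the 24-hour datasheet and the REDCap form. No extra visit or participants are needed, and treatment does not change. The one downside is that direct questioning will raise the recorded event rate in both arms, which should be said when the results are reported.
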